2 OBJECTIVES

2.1 Study Objectives

Primary:

Safety

1. To evaluate the safety and reactogenicity of three different dose concentrations of *Na-APR-1* (M74)/Alhydrogel® co-administered with *Na-GST-1*/Alhydrogel® in healthy Gabonese children.

Secondary:

Immunogenicity

2. To determine the doses of co-administered *Na-APR-1* (M74) and *Na-GST-1* that result in the highest levels of IgG against these vaccine antigens approximately 14 days after the third vaccination.

Tertiary:

Immunogenicity

1. To assess and compare the duration of antibody responses to *Na-GST-1* and *Na-APR-1* (M74).
2. To assess the level of IgG1-4 subclass responses to *Na-APR-1* (M74) and *Na-GST-1*.

Exploratory:

Immunogenicity

1. To assess the cellular immune responses to the *Na-GST-1* and *Na-APR-1* (M74) antigens following immunization.
2. To assess the impact of co-administered *Na-GST-1* and *Na-APR-1* (M74) on the production of memory B cells specific for each antigen.
3. To assess the production of memory B cells specific for each vaccine antigen compared to metabolomic changes before and after vaccination.
4. To characterize the metabolite composition in urine and serum during the course of immunization and assess the changes on metabolite profiles related to each dose of co-administration of *Na-GST-1* and *Na-APR-1* (M74).

2.2 Study Outcome Measures

2.2.1 Primary Outcome Measures

Safety

The following parameters will be evaluated for each dose of *Na-APR-1* (M74) co-administered with *Na-GST-1*:

1. Frequency of solicited injection site and systemic reactogenicity, graded by severity, on the day of each study vaccination through 14 days after each study vaccination.
2. Frequency of study vaccine-related serious adverse events from the time of the first study vaccination through approximately 9 months after the last study vaccination.
3. Frequency of clinical safety laboratory adverse events.
4. Frequency of unsolicited adverse events, graded by severity, from the time of each study vaccination through approximately 1 month after each study vaccination.
5. Frequency of new-onset chronic medical conditions through approximately 9 months after the third study vaccination.
6. Frequency of Adverse Events of Special Interest through approximately 9 months after the third study vaccination.

2.2.2 Secondary Outcome Measure

Immunogenicity

The following parameter will be evaluated for each dose of *Na-APR-1* (M74) co-administered with *Na-GST-1*:

1. The IgG level as measured by a qualified indirect enzyme-linked immunosorbent assay (ELISA) for each vaccine antigen approximately 14 days after the third vaccination.

2.2.3 Tertiary Outcome Measures

Immunogenicity

The following parameters will be evaluated for each dose of *Na-APR-1* (M74) co-administered with *Na-GST-1*:

1. The IgG antibody response as measured by a qualified indirect ELISA at approximately 7, 14, and 28 days after each vaccination, and approximately 3 and 6 months after the third dose.
2. The IgG subclass levels (IgG1, IgG3, and IgG4) against the vaccine antigens by indirect ELISA approximately 14 days after the third vaccination.

3. The IgG1-4 subclass levels as measured by indirect ELISA on each day of vaccination, approximately 28 days later, and approximately 3 and 6 months after the final vaccination.

2.2.4 Exploratory Outcome Measures

The following parameters will be evaluated for each dose of *Na-APR-1* (M74) co-administered with *Na-GST-1*:

1. Cellular immune response will be measured by a qualified indirect ELISA at approximately on days of vaccination, and then 7, 14, and 28 days after each vaccination, and approximately 3 and 6 months after the third dose.
2. Metabolomic profiles before vaccination, on days of vaccination, approximately 7 and 28 days following each vaccination, and 6 months after the third dose.

3 STUDY DESIGN

The study will be conducted as a randomized, placebo-controlled, double-blind Phase 1 dose-escalating clinical trial in healthy children between the ages of 6 and 10 years, inclusive, living in the hookworm-endemic area of Lambaréné, Gabon. The study is designed to evaluate the safety, reactogenicity, and immunogenicity of Na-GST-1/Alhydrogel® co-administered with Na-APR-1 (M74)/Alhydrogel®, as compared to the hepatitis B vaccine, in this age group.

Prior to beginning study-related activities, the consent and cooperation of representative community members will be sought, after which parents of potential pediatric participants will be invited to learn about the study and consent to the participation of their child. After a parent or legal representative provides written informed consent for the child's participation and passes the informed consent comprehension questionnaire, the child will undergo eligibility screening, including a complete medical history, physical examination, hematology testing, liver and renal function testing, HIV antibody testing, Hepatitis B and C serology, and urinalysis. In addition, a fecal examination will be performed for ova and parasites, and urine will be examined for *S. haematobium* ova. All clinically significant abnormalities will be reviewed with parents/legal guardians and referral of the child for follow-up care will be provided. After screening, those children determined to be eligible, based on the inclusion and exclusion criteria, will be invited to participate in the study.

Sixty children will be progressively enrolled into 1 of 3 Groups over a projected 3-month enrollment period, with each child followed for 9 months after the final injection (i.e., until Study Day 380 for those receiving vaccinations according to a 0,2,4-month schedule and until Study Day 448 for those receiving vaccinations according to a 0,2,6-month schedule). Group enrollment will be done in an open sequential fashion, whereas within each Group, investigational product (IP) assignment and vaccination will be done in a randomized double-blind fashion.

60 subjects will be enrolled into 3 groups of 20:

The first 20 subjects will be recruited and enrolled into Group 1:

- Group 1 double-blind IP allocation (n=20):
 - 16 subjects will receive 10µg Na-APR-1 (M74) plus 5µg GLA-AF delivered by IM injection in the deltoid muscle, with 10µg Na-GST-1 administered IM in the alternate arm.
 - 8 will be vaccinated according to a 0,2,4-month schedule
 - 8 will be vaccinated according to a 0,2,6-month schedule
 - 4 subjects will receive hepatitis B vaccine comparator:
 - 2 will be vaccinated according to a 0,2,4-month schedule
 - 2 will be vaccinated according to a 0,2,6-month schedule
- Group 2 double-blind IP allocation (n=20):
 - 16 subjects will receive 30µg Na-APR-1 (M74) plus 5µg GLA-AF delivered by IM injection in the deltoid muscle, with 30µg Na-GST-1 administered IM in the alternate arm.
 - 8 will be vaccinated according to a 0,2,4-month schedule

- 8 will be vaccinated according to a 0,2,**6**-month schedule
- 4 subjects will receive hepatitis B vaccine comparator:
 - 2 will be vaccinated according to a 0,2,**4**-month schedule
 - 2 will be vaccinated according to a 0,2,**6**-month schedule
- **Group 3 double-blind IP allocation (n=20):**
 - 16 subjects will receive 100 μ g *Na-APR-1* (M74) plus 5 μ g GLA-AF delivered by IM injection in the deltoid muscle, with 100 μ g *Na-GST-1* administered IM in the alternate arm.
 - 8 will be vaccinated according to a 0,2,**4**-month schedule
 - 8 will be vaccinated according to a 0,2,**6**-month schedule
 - 4 subjects will receive hepatitis B vaccine comparator:
 - 2 will be vaccinated according to a 0,2,**4**-month schedule
 - 2 will be vaccinated according to a 0,2,**6**-month schedule

As with other aluminum hydroxide-adsorbed vaccines, hypersensitivity reactions would be expected to occur within the first 24 hours after receipt of either of the two vaccines, and other severe local or systemic reactions within 72 hours of vaccination. Children will therefore be observed for immediate reactions following each vaccination for at least 1 hour, and will have a clinical assessment either in their home or at the study clinic on Days 1, 3, 7, and 14 following each vaccination. See **Appendix A** for the schedule of clinical and laboratory evaluations.

In order to review safety data at each dose of *Na-APR-1* (M74)/Alhydrogel[®] prior to testing it in combination with the point-of injection addition of GLA-AF, and to review safety data at each dose of *Na-APR-1* (M74)/Alhydrogel[®] prior to dose escalation, Groups will be enrolled and vaccinated in a staggered fashion. Conference calls between the investigators and the Safety Monitoring Committee (SMC) will be scheduled within the week prior to beginning vaccinations in Groups 2 and 3. A cumulative safety report will be submitted to the SMC before beginning vaccinations in these Groups that will include safety data from at least the first 14 days after vaccination of all subjects in the preceding Group. Written approval (via fax or email) to proceed to vaccinations of Groups 2 and 3 must be obtained from the SMC.

The SMC and Independent Medical Monitor will have access to the randomization code for the study, as they may wish to review the data in an unblinded fashion should significant safety questions arise prior to the final unblinding. The trial will not proceed to the next dose Group if any of the stopping criteria listed in **Section 8.5** are met or, in the clinical judgment of the SMC or the Independent Medical Monitor the next higher dose would pose an unacceptable safety risk to the subjects.

4 STUDY ENROLLMENT AND WITHDRAWAL

Only children who meet all of the inclusion and none of the exclusion criteria will be eligible for enrollment into this study. No exemptions will be granted.

A total of 60 children will be enrolled. The study population will be enrolled from in and around Lambaréné.

Parents/legal guardians who agree to the participation of their child will first provide written informed consent and take a true/false comprehension questionnaire. The questionnaire will be administered orally in the case of illiterate volunteers, and for both written and oral questionnaires study staff will use incorrect answers to identify aspects of the study that require clarification and focus on those areas of the informed consent form for further review with the volunteer. All questionnaire questions must be answered correctly, and the informed consent form signed, prior to study screening and enrollment. Parents or legal guardians who are unable to read will place an imprint of their finger in the place of a signature; in addition, an independent witness, who is not a member of the study team, will sign the consent form to attest that the informed consent form was read to the parent/legal guardian, their questions were answered, and the parent/legal guardian answered all comprehension questions correctly. The original signed informed consent form for each parent/guardian will be maintained as part of that child's study records. A copy of the informed consent form will be provided to every parent/guardian.

Screening can occur up to 90 days prior to enrollment; enrollment/randomization, and administration of first dose of study products will occur on the same day.

4.1 Subject Inclusion Criteria

1. Males or females between 6 and 10 years, inclusive, who are long-term residents of the study area.
2. Good general health as determined by means of the screening procedure.
3. Assumed availability for the duration of the trial (up to 15 months).
4. Willingness of parent or legal guardian for child to participate in the study as evidenced by signing the informed consent document in combination with the child assent form.
5. Negative for hookworm during screening, or if found to be infected with hookworm, has completed a course of three doses of albendazole.

4.2 Subject Exclusion Criteria

1. Inability of parent/legal guardian to correctly answer all questions on the informed consent comprehension questionnaire.
2. Evidence of clinically significant neurologic, cardiac, pulmonary, hepatic, rheumatologic, autoimmune, diabetes, or renal disease by history, physical examination, and/or laboratory studies.
3. Known or suspected immunodeficiency.
4. Laboratory evidence of liver disease (alanine aminotransferase [ALT] greater than 1.25-times the upper reference limit).

5. Laboratory evidence of renal disease (serum creatinine greater than 1.25-times the upper reference limit, or more than 1+ protein, or more than trace blood on urine dipstick testing with the exception of greater than trace blood detected in females during menses).
6. Laboratory evidence of hematologic disease (absolute leukocyte count $<4500/\text{mm}^3$; absolute leukocyte count $>13.0 \times 10^3/\text{mm}^3$; hemoglobin $<9.5 \text{ g/dl}$; or, platelet count $<140,000/\text{mm}^3$).
7. Other condition that in the opinion of the investigator could jeopardize the safety or rights of a child participating in the trial or would render the child unable to comply with the protocol.
8. Participation in another investigational vaccine or drug trial within 30 days of starting this study or for the duration of the study.
9. History of a severe allergic reaction or anaphylaxis.
10. Severe asthma as defined by the need for daily use of inhalers or emergency room/clinic visit or hospitalization within 6 months of the child's planned first vaccination in the study.
11. Positive for HCV.
12. Positive for HBsAg.
13. Positive for HIV infection.
14. Use of corticosteroids (excluding topical or nasal) or immunosuppressive drugs within 30 days of starting this study or expect to use for the duration of the study.
15. Receipt of a live vaccine within past 4 weeks or a killed vaccine within past 2 weeks prior to entry into the study.
16. History of a surgical splenectomy.
17. Receipt of blood products within the 6 months prior to entry into the study.
18. Previous receipt of a primary series (three doses according to a 0, 1, and 6 -12 month schedule) of the hepatitis B vaccine.

4.3 Vaccine Assignment Procedures

4.3.1 Randomization Procedures

Parents/guardians of eligible children will be asked to bring them to the clinic on the scheduled day of enrollment into the study (Day 0). If required, transportation to the clinic will be provided free-of-charge. One or 2 additional eligible children above the number to be enrolled into a given Group may be scheduled as Day 0 visit alternates, if possible. After undergoing a clinical interview and physical examination to ensure that they remain eligible for participation in the study, that they have had blood collected for safety clinical laboratory and baseline immunogenicity assessments, children will be randomized and enrolled in the order that they present for vaccination.

Within each group, randomization will be done through use of a randomization code, furnished to the study vaccine manager by the data management center (AIGHD). Access to the randomization list will be exclusively limited to the study vaccine manager and assistant. Between vaccination days, the randomization list will be stored in a locked cabinet. The study vaccine manager and assistant will be unblinded, but will not be involved in further evaluation of study subjects or assessment of adverse events. Children will not be considered enrolled in the study until they have received their first dose of vaccine. In the event that a child is randomized but not enrolled on the day of first vaccination, they will be replaced with an eligible alternate. Enrolled children that leave the study for any reason following first vaccination will not be replaced. Any alternates not vaccinated will be invited to participate as members of the next Group. Any Group

3 alternates not vaccinated, and therefore not enrolled in the study, will be offered vaccination with a non-study, licensed vaccine such as the tetanus toxoid or influenza vaccine.

4.3.2 Allocation of vaccination schedule and vaccine randomization

Within each cohort the first 10 participants will receive the 0,2,4-month vaccination schedule and the last 10 will receive the 0,2,6-month schedule. The participants will be randomized to either the experimental group, receiving *Na-APR-1*(M74) plus 5 µg GLA-AF co-administered with *Na-GST-1*, or randomized to the control group who will receive HBV co-administered with sterile saline. In addition, there will be a randomization to assign left/right arm vaccination for the first injection, the arms will be alternated for the second and third sets of vaccinations. The Randomization list will thus only be used on Day 0 for a particular participant.

The vaccination manager assigns the Study ID when the vaccines are being prepared for that particular participant. The Study ID is written onto the syringes and then the vaccinator writes the Study ID onto the CRF.

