1.2.2 Rationale for Doses and Dose Schedule to be Studied

Na-APR-1 (M74)/Alhydrogel® and *Na-GST-1*/Alhydrogel® (with or without GLA-AF) have been tested at the same field site as that proposed in the study described in this protocol, in healthy hookworm-exposed adults without any observed safety concerns. Therefore, in the study described in this protocol, these two vaccine products will be administered in escalating doses, to school-age children who live in an area where hookworm is endemic. Doses of 10, 30 and 100 µg of *Na-APR-1* (M74) and *Na-GST-1*/Alhydrogel® were selected for evaluation based on preclinical studies and to maintain an equal fold-increase in the amount of antigen. The 10 µg dose was also selected as the lowest dose for clinical trials due to the difficulty in precisely dispensing lower volumes (both vaccine antigens have been formulated at a protein concentration of 100µg/ml). Selection of the maximum 100 µg doses of *Na-GST-1* and *Na-APR-1* (M74) is based on the safety and immunogenicity data from the Phase 1 studies of these antigens that have been conducted in adults, in which this was the maximum dose tested.

To date, up to 100 µg *Na-APR-1* (M74)/Alhydrogel® administered with 5 µg GLA-AF has been very well tolerated in healthy adults, with no observed vaccine-related Serious Adverse Events and only mild to moderate local injection site pain and tenderness being the most commonly reported adverse events. However, the addition of GLA-AF to *Na-GST-1*/Alhydrogel did not significantly increase IgG levels to the *Na-GST-1* antigen. Therefore, GLA-AF will not be tested further in combination with *Na-GST-1*/Alhydrogel.

For the study proposed in this clinical protocol, each child will be vaccinated three times, on Days 0, 56, and 112 or 180. On each vaccination day each child will receive two injections, one injection per arm. This vaccination schedule was selected to coordinate with the Expanded Program on Immunization as the human hookworm vaccine is intended to target children, including eventually infants. Two different vaccination schedules are being tested (i.e., 0, 2, 4 months vs. 0, 2, 6 months) to determine the optimal immunogenicity.

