Investigators will be unblinded after all subjects have had their study Day 208 visit (i.e., 1 month after the final vaccination for those children randomized to receive vaccines on the 0, 2, and 6-month schedule), the safety and secondary immunogenicity outcomes (i.e., anti-Na-GST-1 and anti-Na-APR-1 (M74) IgG antibody results by ELISA) have been monitored and entered into the database, and the database has been “soft-locked” for interim analysis. After this point, the study will be single-blinded (i.e., subjects will remain blinded to what products they received). The principal justification for unblinding the investigators before the final study visit has been completed is that the safety and immunogenicity data acquired during the vaccination phase of the study will be crucial in guiding the human hookworm vaccine clinical development plan, and we feel that to make an informed decision as to whether or not to proceed to pediatric trials, we must first assess the unblinded data in a timely fashion.

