1. Perform basic history and physical exam (including injection site), emphasizing examination of any acute complaints.
2. Record vital signs.
3. Obtain blood for anti-Na-GST-1 and anti-Na-APR-1 (M74) humoral and cellular immunology assays.
4. Obtain a urine sample for metabolomics study.

Study Day 70 (14 +/- 2 days after Second Vaccination)

1. Perform basic history and physical exam (including injection site), emphasizing examination of any acute complaints.
2. Record vital signs.
3. Obtain blood for hematology, biochemistry, anti-Na-GST-1 and anti-Na-APR-1 (M74) humoral and cellular immunology assays.
4. Obtain a urine sample for metabolomics study.

Study Day 84 (28 +/- 4 days after Second Vaccination)

1. Perform basic history and physical exam, emphasizing examination of any complaints.
2. Record vital signs.
3. Obtain blood for anti-Na-GST-1 and anti-Na-APR-1 (M74) humoral and cellular immunology assays.
4. Obtain a urine sample for metabolomics study.

Study Day 112 +/- 14 [Groups 1a, 2a, & 3a] or 180 [Groups 1b, 2b, & 3b]

(Day of Third Vaccination)

1. Perform basic history (including concomitant medications) and physical exam (including injection site), emphasizing examination of any acute complaints.
2. Obtain blood for hematology, biochemistry, anti-Na-GST-1 and anti-Na-APR-1 (M74) humoral and cellular immunology assays.
3. Obtain a urine sample for metabolomics study.
4. Record vital signs.
5. Administer the vaccine.
6. Observe for at least 1 hour after vaccination to evaluate for immediate adverse reactions.

Study Day 113/181 (1 day after Third Vaccination)

1. Perform basic history and physical exam (including injection site), emphasizing examination of any acute complaints.
2. Record vital signs.
3. Obtain a urine sample for metabolomics study.

Study Day 115/183 (3 +/- 1 days after Third Vaccination)

1. Perform basic history and physical exam (including injection site), emphasizing examination of any acute complaints.
2. Record vital signs.
3. Obtain a urine sample for metabolomics study.

Study Day 119/187 (7 +/- 1 days after Third Vaccination)

1. Perform basic history and physical exam (including injection site), emphasizing examination of any acute complaints.
2. Record vital signs.
3. Obtain blood for anti-Na-GST-1 and anti-Na-APR-1 (M74) humoral and cellular immunology assays.
4. Obtain a urine sample for metabolomics study.

Study Day 126/194 (14 +/- 2 days after Third Vaccination)

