10.3 Final Analysis Plan

The purpose of this trial is to estimate AE rates and patterns of immune response as well as to compare these rates and patterns when Na-GST-1/Alhydrogel® and Na-APR-1 (M74)/Alhydrogel® are administered separately or when they are co-administered.

This section briefly describes the statistical methods to be used; a detailed analytical plan will fully describe the methods. The analytical plan will discuss the planned approaches to missing data. Deviations from the original analytical plan will be thoroughly documented and reported to the Sponsor.

Descriptive and hypothesis-testing approaches will be used to meet the protocol objectives as stated in **Section 3**. Estimates will be presented with their 95% confidence intervals. Formal statistical tests, as outlined below, will be used to compare doses. Statistical tests will use a two-sided significance level of 5%.

Primary Objective: To evaluate the safety and reactogenicity of three different dose concentrations of *Na-APR-1* (M74)/Alhydrogel® co-administered with *Na-GST-1*/Alhydrogel® in healthy Gabonese children.

AEs will be coded according to Medical Dictionary of Regulatory Activities (MedDRA™) preferred terms. The frequency, severity, and relationship of AEs per each dose of *Na-APR-1* (M74)/Alhydrogel® and *Na-GST-1*/Alhydrogel® compared to Hepatitis B vaccine will be presented in tabular form using the MedDRA™ coded term and organized by MedDRA™ System, Organ, and Class (SOC) designations.

- The frequency of immediate, systemic, and local injection site AEs will be summarized by SOC and preferred term.
- Line listings of clinical and laboratory AEs classified as immediate (within the first 60 minutes), systemic, and local will be displayed in tables stratified by vaccine (i.e., hookworm vs. Hepatitis B vaccines) dose of *Na-APR-1* (M74)/Alhydrogel® and *Na-GST-1*/Alhydrogel®.
- AEs will be summarized by severity and relationship to vaccine by individuals and dose of *Na-GST-1* and *Na-APR-1* (M74).
- The frequency of vaccine-related SAEs will be tallied as well as summarized by body system, by vaccine and dose.

Primary Outcome Measures:

The following summary parameters will be evaluated for each vaccine (hookworm vs. Hepatitis B) and dose of *Na-APR-1* (M74) co-administered with *Na-GST-1*:

1. Frequency of solicited injection site and systemic reactogenicity, graded by severity, on the day of each study vaccination through 14 days after each study vaccination.

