2. Frequency of study vaccine-related serious adverse events from the time of the first study vaccination through approximately 9 months after the last study vaccination.
3. Frequency of clinical safety laboratory adverse events.
4. Frequency of unsolicited adverse events, graded by severity, from the time of each study vaccination through approximately 1 month after each study vaccination.
5. Frequency of new-onset chronic medical conditions through approximately 9 months after the third study vaccination.
6. Frequency of Adverse Events of Special Interest through approximately 9 months after the third study vaccination.

Analysis Plan:

- a. The proportion of participants with at least one injection site AE will be compared by vaccine and dose cohort. We will test the null hypotheses that the type and number of adverse events is the same across all groups by Fisher's exact test.
- b. Laboratory results (hematological and clinical chemistry) will be examined for trends over time and any clinically significant values for individuals will be reported.

Secondary Objective: To determine the doses of co-administered Na-APR-1 (M74) and Na-GST-1 that result in the highest levels of IgG antibody approximately 14 days after the third vaccination.

Secondary Outcome Measure:

The following parameters will be evaluated for each dose of Na-APR-1 (M74) co-administered with Na-GST-1:

1. The IgG level by a qualified indirect ELISA approximately 14 days after the third vaccination.

Analysis Plan:

- a. The proportion of participants with detectable anti-Na-GST-1 and anti-Na-APR-1 (M74) responses will be summarized as a descriptive measure.
- b. IgG levels will be displayed graphically by study group using notched box plots.
- c. Geometric mean antibody responses will be compared between vaccine formulation and dose groups. Comparisons between groups will be made by a one-way analysis of variance (ANOVA) with pair-wise comparisons between groups made by contrasts.
- d. Geometric mean antibody responses for each antigen will be compared using a regression model with main effects for the doses of Na-APR-1 (10, 30 or 100 μ g), and Na-GST-1 (10, 30 or 100 μ g).

Tertiary Objective 1: To assess and compare the duration of antibody responses to Na-GST-1 and Na-APR-1 (M74).

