Tertiary Outcome Measure 1: The IgG antibody response, by indirect enzyme-linked immunosorbent assay (ELISA) at approximately 7, 14, and 28 days after each vaccination, and approximately 3 and 6 months after the third dose.

Analysis Plan:

- a. The proportion of participants with detectable anti-Na-GST-1 and anti-Na-APR-1 (M74) responses will be summarized as a descriptive measure.
- b. Antigen-specific IgG levels will be displayed graphically by study group using notched box plots at each time point.
- c. Geometric mean antibody responses will be compared between vaccine and dose groups at each time point. Comparisons between groups will be made by a one-way

analysis of variance (ANOVA) with pair-wise comparisons between groups made by contrasts.

- d. Percent change in IgG antibody levels from days of vaccination to days 7, 14 and 28 will be compared between vaccine formulation and dose groups. Values will be reported with 95% confidence intervals.
- e. Percent change in IgG antibody levels from vaccination day #1 to #2, and from vaccination day #2 to #3 will be compared between vaccine formulation and dose groups to assess the sustainability of the response from trough to trough. Values will be reported with 95% confidence intervals.
- f. Percent change in IgG antibody levels from the peak following the third vaccination, to 3 and 6 months after the third vaccination. Values will be reported with 95% confidence intervals.
- g. Geometric mean antibody responses for each antigen will be compared using a regression model at each time point with main effects for the doses of *Na-APR-1* (M74) (10, 30 or 100 μ g) and *Na-GST-1* (10, 30 or 100 μ g)
- h. A longitudinal model will be built to describe the IgG levels over time. Using a longitudinal panel model, differences in antibody isotype levels by dose of *Na-APR-1* (M74) and *Na-GST-1* will be explored. This will take account of the correlation between measurements on the same participant.

Tertiary Objective 2: To assess the distribution of IgG subclass responses to *Na-APR-1* (M74) and *Na-GST-1*.

Tertiary Outcome Measure 2: The IgG subclass distribution (IgG1, IgG3, and IgG4) by indirect ELISA approximately 14 days after the third vaccination.

Tertiary Outcome Measure 3: The IgG1-4 subclass distribution by ELISA on each day of vaccination, approximately 28 days later, and approximately 3 and 6 months after the final vaccination.

Analysis Plan:

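### Vaccination schedule (0,2,4 vs 0,2,6 months) follows arrival order rather than randomisation, and Section 10 names no schedule estimate, although comparing schedules is the stated reason for running two

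*Combined protocol and SAP*

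**What the plan says.** Section 4.3.2 allocates schedule by rank within the cohort: "Within each cohort the first 10 participants will receive the 0,2,4-month vaccination schedule and the last 10 will receive the 0,2,6-month schedule". Rank comes from Section 4.3.1, where "children will be randomized and enrolled in the order that they present for vaccination". What Section 4.3.2 does randomise is the product (hookworm vaccines or hepatitis B vaccine plus saline) and the arm used for the first injection. Section 4.3.3, in explaining the timing of unblinding, refers to "children randomized to receive vaccines on the 0, 2, and 6-month schedule".

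The purpose of having two schedules is given in Section 1.2.2: "Two different vaccination schedules are being tested (i.e., 0, 2, 4 months vs. 0, 2, 6 months) to determine the optimal immunogenicity". No objective in Section 2.1 and no outcome measure in Section 2.2 compares them.

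The comparisons named in Section 10 are by vaccine, formulation or dose. For the secondary IgG outcome, "Geometric mean antibody responses will be compared between vaccine formulation and dose groups", followed by a regression on the two antigen doses. Tertiary analysis (e) in Section 10.3 looks at percent change in IgG "from vaccination day #2 to #3 will be compared between vaccine formulation and dose groups to assess the sustainability of the response". Schedule is visible in Section 10 only as paired visit days such as 126/194. Section 10.3 adds that "a detailed analytical plan will fully describe the methods"; that plan is not among the documents supplied.

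**The concern.** Schedule is completely tied to order of presentation, and in the same direction in every cohort, so any order effect accumulates over the three groups instead of cancelling. The protocol contains routes by which order could matter. Under Section 6.1, children treated for parasites must wait 14 days before enrolment and so may tend to enter later. Under Section 4.3.1, unvaccinated alternates roll into the next group already screened and so may enter early. Neither route is shown to operate.

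Two things are at stake. First, the trial runs two schedules to answer a question it states, but as written it could not attribute an IgG difference to the dosing interval, and no estimate of that difference is named. Second, schedule enters a planned analysis without acknowledgement: the change from second to third vaccination is summarised by vaccine and dose only, while the time between those vaccinations depends on schedule.

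**Working it through.** The plan gives no figure for the schedule comparison. Its only sample-size calculation is the event-detection table in Section 10.1, which reproduces: at N = 20 and a true rate of 10%, 1 − 0.90^20 = 87.84%, and the other 14 cells also match 1 − (1 − p)^N. The N = 30 column equals the number of children per schedule, but Section 10.1 attaches it to a contrast with *Na-APR-1* alone, so it does not bear on schedule.

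**Inputs from the documents.** Each dose has 8 hookworm vaccinees per schedule (Section 3), giving 24 vs 24 by schedule and 16 per dose. Tests are two-sided at 5% (Section 10.3). The second vaccination is on Day 56 and the third on "Study Day 112 +/- 14 [Groups 1a, 2a, & 3a] or 180 [Groups 1b, 2b, & 3b]" (Section 6.3).

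**Assumptions, because the documents give no values.** SD of log10 IgG 0.5 (range 0.4–0.6); antibody half-life 60 days (range 40–90) with simple exponential decay; schedule effect 0.5–1.0 SD; no dropout.

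1. **Interval in tertiary analysis (e).** Groups 1a–3a: 112 − 56 = 56 days. Groups 1b–3b: 180 − 56 = 124 days. The ratio is 124/56 = 2.2 and the difference 68 days. Decay over those extra 68 days lowers the pre-dose-3 trough by 2^(68/H): 2.2-fold at H = 60 days, 3.2-fold at 40 and 1.7-fold at 90. The two values of 2.2 are separate quantities: the interval ratio is documented, the trough ratio depends on the assumed half-life.

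2. **Effect on dose comparisons.** Each dose has the same 8:8 schedule mix, so leaving schedule out does not bias the dose contrast. It moves the schedule effect into the error term. For a balanced two-level factor of size d SD, the residual SD grows by about √(1 + d²/4): 1.031 at d = 0.5 and 1.118 at d = 1.0. The 95% CI factor for a 16 vs 16 dose ratio (48 − 3 = 45 df, t = 2.014) is 10^(2.014 × 0.5 × √(2/16)) = 2.27 with no omitted effect. It becomes 2.33 at d = 0.5 and 2.5 at d = 1.0. With the schedule term fitted (44 df) it returns to 2.27.

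3. **Precision of a schedule estimate, if schedule were randomised.** Pooled over doses, 24 vs 24 with dose and schedule as factors (44 df), the CI factor is 10^(2.015 × SD × √(2/24)) = 1.71, 1.95 and 2.23 at SD 0.4, 0.5 and 0.6. Within one dose, 8 vs 8 (14 df), it is 2.69, 3.44 and 4.40.

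4. **Illustration of arrival-order bias.** The plan contains no schedule test and the documents give no basis for the size of an imbalance, so this shows sensitivity only. Suppose arrival order alone shifted mean log10 IgG by 0.1 or 0.2 (1.26- or 1.58-fold). A two-sample t test on 24 vs 24 (46 df, noncentrality shift/(SD × √(2/24))) would then reject as follows, against a nominal 5%:

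| SD | shift 0.1 | shift 0.2 |
|---|---|---|
| 0.4 | 13.6% | 39.6% |
| 0.5 | 10.4% | 27.4% |
| 0.6 | 8.7% | 20.4% |

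**The case against.** The strongest reply is that the order rule is openly stated, under a heading that separates schedule allocation from vaccine randomisation. The word in Section 4.3.3 may simply be carried-over text: that section also mentions a Group 4 in a three-group trial and a decision on whether to start paediatric trials. Schedule is a rationale, not a listed objective, and Section 10.1 says the trial is not powered for group comparisons. The deferred analytical plan may supply a schedule contrast, and the box plots by study group could be read as showing subgroups a and b. No passage links arrival order to antibody response; Section 1.1.8 found no association between antibody presence and current infection. Dose contrasts are unbiased, including in analysis (e). Finally, the randomisation list is restricted to the unblinded vaccine manager and assistant, so schedule would need its own release route.

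Much of this stands. The contradiction in Section 4.3.3 may be a slip. Confounding is possible, not demonstrated, and step 4 is no evidence that it exists. The absence of an estimate can be asserted only for the documents supplied. It does not remove the point. A later plan can add a model term but cannot randomise children after the fact. Low power is a reason to report an estimate with its interval, not to accept an avoidable non-random allocation. A box plot is a display, not an estimate. Releasing schedule without product is a small administrative step.

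**Conclusion.** The concern holds and should be fixed. Schedule is assigned by arrival order, one phrase says otherwise, and the stated schedule question has neither protection by randomisation nor a named estimate in these documents. The size and direction of any arrival-order bias cannot be derived from them.

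The documented consequence is a sustainability summary that mixes 56-day and 124-day intervals and describes neither schedule. The conditional consequences are modest: under the assumed SD of 0.5, a dose-ratio CI factor of 2.33–2.5 instead of 2.27 if schedule has an effect of 0.5–1.0 SD. Randomising would not make the schedule comparison precise (a factor of about 1.95 pooled, 3.4 within a dose), but it would make the estimate interpretable at the same sample size. The vaccine and dose comparisons are not biased by this defect.

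**What to change.** **Before enrolment:**
- Add schedule to the Day 0 randomisation list within each group of 20, keeping the cells at 8 vaccine and 2 control children per schedule, with a way to release schedule to visit staff without revealing product.
- In Section 10.3, analyse log IgG 14 days after the third vaccination among hookworm vaccinees with dose and schedule as factors. Report the schedule ratio pooled over doses with its 95% CI, labelled a low-precision estimate.
- Report the second-to-third vaccination change in tertiary analysis (e) separately by schedule.
- Make Sections 4.3.2 and 4.3.3 agree.

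**If a cohort is already enrolled:** correct the wording in Section 4.3.3, label the schedule comparison non-randomised and descriptive, adjust it for Day 0 IgG (blood for the antibody assays is drawn from every child at Day 0, Section 6.2), and still split analysis (e).

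**Cost:** regenerating the list, one model term, one split table and a separate schedule release. Vaccination and visit days are the same through Day 84 in Appendices A1 and A2, so interleaving the two schedules affects logistics only from Day 112. No extra children, samples or visits are needed.
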